#### 3.2.3. Exploratory

None.

# **3.3.** Study Definitions and Derived Variables

"Baseline" value of any safety or efficacy parameter refers to the last value collected prior to receipt of first study vaccination.

For individual subjects, fold rise will be calculated as the ratio of:  $\frac{post-vaccination value}{pre-vaccination value}$ , where pre-vaccination value is the result obtained at Day 1 prior to the first study vaccination.

For calculations of geometric mean and fold rise of assay results, individual results below the LLOQ will be imputed as  $\frac{1}{2} \times \text{LLOQ}$ . The LLOQ for each assay was defined by the central laboratory as follows: TNA ED50: 33; TNA NF50: 0.064; anti-PA IgG: 9.27 µg/mL.

For subjects with baseline assay result  $\geq$  LLOQ, seroconversion is defined as at least a 4-fold increase over baseline value. For subjects with baseline assay result < LLOQ, seroconversion is defined as achieving a post-baseline result of at least 4 × LLOQ; this ensures that subjects with undetectable baseline antibody levels have achieved at least a 4-fold increase over baseline, regardless of the baseline result reported.

Putative seroprotection is defined as  $NF_{50} \ge 0.56$ .

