- 8. Have a history of receipt or plan to receive, while enrolled in this study, a licensed or unlicensed anthrax vaccine (except for the vaccines under study herein).
- 9. Have a history of PIMMCs.

Refer to Appendix B: Adverse Events of Special Interest

10. Have a history of alcohol or drug abuse within 5 years prior to study enrollment or test positive on the screening urine test for drugs of abuse.

11. Have any diagnosis, current or past, of schizophrenia, bipolar disease, or other psychiatric diagnosis that may interfere with participant compliance or safety evaluations.

- 12. Have been hospitalized for psychiatric illness, history of suicide attempt, or confinement for danger to self or others within 5 years prior to study vaccination.
- 13. Received or plan to receive a licensed, live vaccine within 30 days before or after each study vaccination.
- 14. Received or plan to receive a licensed, inactivated vaccine within 14 days before or after each study vaccination.
- 15. Have a known history of documented anthrax disease or suspected exposure to anthrax.
- 16. Received immunoglobulin or other blood products, except Rho(D) immunoglobulin, within 90 days prior to study vaccination.
- 17. Received an experimental agent within 30 days prior to the study vaccination or expect to receive another experimental agent during the trial-reporting period.

18. Are participating or plan to participate in another clinical trial with an interventional agent that will be received during the trial-reporting period.

- 19. Female participants who are breastfeeding or plan to breastfeed from the time of the first study vaccination through 30 days after the second study vaccination.
- 20. Planning to donate blood within 4 months following second vaccination.
- 21. Planned elective surgery during study participation.

<sup>10Note that a prospective participant with a positive urine for drugs of abuse test for a medication reported by the participant and used to treat a condition that does not make them otherwise ineligible, may be permitted to enroll, at the discretion of the investigator or his designee.

<sup>11As determined by the site PI or appropriate sub-investigator.

<sup>12Including vaccine, drug, biologic, device, blood product, or medication.

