#### 3.2.2. Secondary

Immunogenicity:

- Geometric mean titer and 95% confidence intervals of antibodies assayed by toxin neutralization assay (ED50 and NF50) and anti-PA IgG by ELISA in each study group before vaccination and on approximately Days 8, 15, 22, 29, 64, 195, and 380.
- Proportion and 95% confidence intervals of participants in each study group with seroconversion for antibodies detected by TNA and ELISA (defined as a ≥4-fold increase over baseline levels, or a ≥4-fold increase over the lower limit of quantification [LLOQ] if the baseline value is < LLOQ) on approximately Days 8, 15, 22, 29, 64, 195, and 380.
- Proportion and 95% confidence intervals of participants in each study group with putative seroprotection (defined as NF50 ≥ 0.56) before vaccination and on approximately Days 8, 15, 22, 29, 64, 195, and 380.

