# 5. SAMPLE SIZE CONSIDERATIONS

This study is planned to enroll a total of 40 subjects, with 20 subjects in each study arm. This phase I study is not designed to test a formal null hypothesis. Rather, it is intended to obtain sufficient data to obtain meaningful estimates of the immune response induced by either vaccine formulation and to uncover any safety issues that occur at a sufficiently high rate that they might be observed in a study of this size. As such, the type one error rate, alpha = 0.05, is not adjusted for multiple comparisons. While this study is not designed to test any specific null hypothesis, the following tables illustrate the precision and power that is available for select estimates and comparisons of interest.

Table 2 indicates the probability of observing one or more safety events, such as solicited injection site or systemic reactogenicity events or an unsolicited AE of a particular type, for a single treatment arm (N=20), and for all enrolled subjects (N=40).

Binomial confidence intervals (CI) are widest (have the least precision) when the response rate is 50%. Table 3 is presented to indicate the worst-case scenario for precision of observed exact (Clopper-Pearson) binomial confidence intervals.

For each of the primary immunogenicity objectives, a power analysis is provided below for testing the following hypotheses with the planned sample size, where  $p_c =$  probability of response in comparator arm; where  $p_c =$  probability of response in experimental arm.

Test for difference in proportion responders:

 $H_0: p_c - p_e = 0$ ; No difference in response probabilities

H1:  $p_c - p_e \neq 0$ ; difference in response probabilities

Table 4 illustrates the minimum detectable differences in the probability of responding (e.g., attaining seroconversion or  $NF_{50} \ge 0.56$  [seroprotection]) between participants who receive AV7909 as the lyophilized formulation or liquid formulation using a two-sided likelihood ratio test with 80% power and alpha = 0.05. It is assumed that up to 10% of subjects (N=2) will be excluded from the per-protocol analysis in each group. Seroconversion rates of 10% to 60% are considered.

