# 8. EFFICACY EVALUATION

Summaries and analysis of immunogenicity data will be presented for the mITT and PP populations. Immune responses in terms of TNA ED50 and NF50, and anti-PA IgG by ELISA will be summarized by study arm at each time point. Descriptive summary statistics by study arm will be provided for all assays and time points, including number of subjects with non-missing results, GMT (geometric mean titer) for TNA results or GMC (geometric mean concentration) for IgG ELISA results, GMFR (geometric mean fold rise from baseline), and percentage of subjects achieving seroconversion (see Section 3.3). Additionally, the percentage of subjects in each study arm achieving putative seroprotection (see Section 3.3) will be assessed at each time point. GMT/GMC and GMFR results will be presented with corresponding 95% confidence intervals (CIs) based on Student's t-distribution. Exact binomial 95% CIs calculated using the Clopper-Pearson method (SAS Proc Freq with a binomial option) will be presented for proportional endpoints. No exploratory immunologic outcomes are anticipated.

Individual TNA ED50, TNA NF50, and anti-PA IgG assay results will be provided in Listing 9.

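### Setting results below the LLOQ to half the LLOQ and then using a t interval makes the GMT/GMC interval too narrow where most results are below the LLOQ, and of zero width if all are.

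*SAP*

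**What the plan says.** SAP 3.3 fixes the handling of low results: "For calculations of geometric mean and fold rise of assay results, individual results below the LLOQ will be imputed as" half the LLOQ. The limits are given there too: "The LLOQ for each assay was defined by the central laboratory as follows: TNA ED 50 : 33; TNA NF 50 : 0.064; anti-PA IgG: 9.27" µg/mL. The substituted constants are therefore 16.5 (ED50), 0.032 (NF50) and 4.635 µg/mL (anti-PA IgG).

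SAP 8 fixes the interval: "GMT/GMC and GMFR results will be presented with corresponding 95% confidence intervals (CIs) based on Student's t-distribution". SAP 3.2.2 asks for the GMT and its interval "in each study group before vaccination and on approximately Days 8, 15, 22, 29, 64, 195, and 380". Tables 21-32 print it at each visit for both arms, and Figures 9-14 draw it as error bars from Day 1.

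On who is enrolled, Protocol 5.1.2 excludes anyone who would "Have a history of receipt or plan to receive, while enrolled in this study, a licensed or unlicensed anthrax vaccine" other than the study vaccines (criterion 8). It also excludes known past anthrax or suspected contact with it (criterion 15) and military service since 1990 (criterion 23).

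The SAP plans no count of results below the LLOQ, no rule for a cell with zero variance, no censored-data method and no sensitivity analysis for the substitution. It does plan reverse cumulative distribution curves for each assay, visit and arm, and a listing of individual results (Listing 9).

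**The concern.** A t interval takes its width from the spread of the values. Substituted values have no spread, so the more of them a cell holds, the more certain its GMT appears, although less has been measured. The substituted geometric mean also cannot fall below half the LLOQ, so when true titres are low it sits too high, with error bars that do not reach down to them.

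This interval is the only uncertainty statement planned for the first-listed secondary endpoint, and the secondary objective is a first comparative estimate of the two formulations. If most results in both arms are below the LLOQ, the figures will show two nearly equal means with short bars. A reader could take the shortness of the bars for precision.

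**Working it through.** **Inputs from the documents.** ED50 LLOQ 33, substituted value 16.5 (SAP 3.3). Student's t 95% interval (SAP 8). Arm size 20 as enrolled, "with 20 subjects in each study arm", and 18 per protocol: "It is assumed that up to 10% of subjects (N=2) will be excluded from the per-protocol analysis in each group" (SAP 5).

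**Inputs assumed.** The documents give no SD for any assay and no share of results below the LLOQ. Log10 SDs of 0.2 to 0.7 and shares of 10% to 99% below were tried, with lognormal titres.

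**The plan's own figures.** None is stated for GMT precision. The nearest, the worst-case binomial intervals in SAP Table 3, reproduce (27.2-72.8 for N=20, 33.8-66.2 for N=40) but concern proportions.

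**Step 1: all values below.** With x = log10 of the result after substitution, the interval is 10^(mean(x) ± t × s/√n). If every x equals log10(16.5), then s = 0 and the result is 16.5 (16.5, 16.5).

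**Step 2: one quantifiable value.** With one of 18 at 33, mean(x) = 1.2175 + 0.3010/18 = 1.2342 and s = 0.3010/√18 = 0.0710. The half-width is 2.110 × 0.0710/√18 = 0.0353, giving 17.1 (15.8, 18.6). With two of 18 at 66 it is 19.2 (15.4, 24.1). Zero width disappears as soon as one value is quantifiable.

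**Step 3: how likely is an all-below arm?** If each person has chance p of being below, it is p^n.

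| p (assumed) | n=18 | n=10 (rough size of a sex or age subgroup per arm) |
|---|---|---|
| 0.99 | 83% | 90% |
| 0.95 | 40% | 60% |
| 0.90 | 15% | 35% |

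**Step 4: partial censoring.** If a share q is below the LLOQ, the true GMT is 33 × 10^(−SD × z_q). At q = 80% (z = 0.842) this is 18.5, 13.8 and 10.3 for SD 0.30, 0.45 and 0.60. At q = 90% (z = 1.282) it is 13.6, 8.7 and 5.6. All but the first lie below the floor of 16.5. Simulated coverage of the nominal 95% interval (n=20, 20,000 arms per scenario):

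| Share below LLOQ | SD 0.30 | SD 0.45 | SD 0.60 |
|---|---|---|---|
| 50% | 91% | 94% | 91% |
| 70% | 93% | 74% | 11% |
| 80% | 92% | 0% | 0% |
| 90% | 0% | 0% | 0% |

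At 90% below, the reported GMT averages 18.3 to 18.9. Mean width relative to the t interval on uncensored values is then 0.42, 0.33 and 0.28. At 75% below (n=18) it is 0.72 for SD 0.3 and 0.56 for SD 0.5. At 50% or less below it is 0.78 to 1.11 across the three SDs in the table.

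**Step 5: wider SD range (n=18, SD 0.2 to 0.7).** The width ratio is 0.26-0.55 at 90% below, 0.49-0.94 at 75%, 0.74-1.24 at 50% and 0.92-1.30 at 25%. Coverage at 50% below falls to 79% for SD 0.2 and 89% for SD 0.7. For SD 0.2 the interval is then too wide, and the failure is bias: a mean GMT of 28.1 against 33.0.

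**Step 6: censored likelihood.** A left-censored lognormal profile-likelihood interval (n=18, SD 0.3 and 0.5, 25% to 75% below) covered 93-96%. At 75% below, 14-15% of arms had fewer than three quantifiable values and were not fitted.

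**Step 7: fold rise.** With baseline below the LLOQ, an ED50 of 66 to 131 gives a fold rise of 66/16.5 = 4.0 to 131/16.5 = 7.9. Seroconversion needs 4 × 33 = 132. If every baseline is below, the GMFR interval is the GMT interval divided by 16.5 and carries no baseline variability.

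**The case against.** A reader might infer that the baseline interval will have zero width and that early-visit intervals are falsely tight in both arms. The documents support neither as fact. Zero width needs every value in the cell to be below the LLOQ, and SAP 3.3 has a seroconversion rule for baselines at or above it. Neither the share below nor the SD at Day 8 or Day 15 is given, and at 50% or less below the interval can be about right or too wide. This part of the objection stands in full.

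A reader might also infer that the bars would make the formulations look alike whatever the true titres. That goes too far. Baseline precedes vaccination. If most values in both arms are below the LLOQ, titres in both are low: the seroprotection cut-off of 0.56 is 0.56/0.064 = 8.75 times the NF50 LLOQ. An arm with mostly quantifiable values would show a higher GMT. The reverse cumulative curves and Listing 9 also let a careful reader see the pile-up, although they do not correct the printed intervals.

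Nor is the gap between GMFR and seroconversion an error. SAP 3.3 explains the 4 × LLOQ rule as a guarantee of a true fourfold rise, and it matches the protocol. GMFR is not a protocol endpoint. A footnote is enough.

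Finally, the simulation favours the likelihood method, because lognormal data are fitted with a lognormal model, and that method was not tested at subgroup size. This argues for a sensitivity analysis, not a replacement. Switching estimator arm by arm at a threshold would harm the comparison. Dropping intervals outright would remove results that Protocol Table 1 names.

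**Conclusion.** The concern holds conditionally. Where all results in a cell are below the LLOQ, the planned interval has exactly zero width; this is arithmetic and needs no assumption. Where about 75% or more are below, it is too narrow in every scenario tried (about 0.3 to 0.7 of the uncensored width for log10 SD 0.30 to 0.60) and often misses the true GMT: coverage 92/0/0% at 80% below and 0% at 90% below, n=20. These sizes rest on assumed SDs, assumed shares and lognormal titres.

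Baseline is the visit where this is to be expected, by inference from the exclusions; Day 8 is possible. At 50% or less below, coverage is about 91-95% for SD 0.30 to 0.60 (lower at SD 0.2 and 0.7 when half are below), so the main method need not change. The effect is confined to GMT/GMC and GMFR. Seroconversion and seroprotection use exact binomial intervals and do not depend on the constant. Safety endpoints and sample size are untouched, and no formal test is planned.

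**What to change.** Amend SAP 3.3 and 8, Tables 21-32 and Figures 9-14:

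1. Add n (%) at or above the LLOQ for each arm and visit, with a Clopper-Pearson interval.
2. When every value in a cell is below the LLOQ, report `<LLOQ` and mark the GMT/GMC interval and error bar as not estimable. This keeps the protocol-named line in the table.
3. Keep half-LLOQ substitution as the main summary. Add a left-censored lognormal likelihood estimate of the GMT/GMC with its interval as a sensitivity analysis, applied to both arms alike at any visit where either arm has a substantial share below the LLOQ. Name that share in the SAP before unblinding; 25% would be cautious, since substitution kept 91% coverage or better at or below it for SD 0.2 to 0.7. State a minimum number of quantifiable values for fitting (three was used here). Flag the t interval as unreliable when more than half the values are below.
4. Footnote that, for baselines below the LLOQ, GMFR divides by half the LLOQ while seroconversion requires 4 × LLOQ, so a fold rise of 4.0 to 7.9 can be recorded as not seroconverted.

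The cost is SAP wording and a little more SAS programming, with no new data. Some early cells will show `<LLOQ` or not estimable instead of an interval.

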# 4. INVESTIGATIONAL PLAN

# 4.1. Overall Study Design and Plan

DMID Protocol 17-0093 is a phase I randomized, parallel-group, double-blind controlled interventional trial in which the safety, tolerability, and immunogenicity of 2 formulations of adjuvanted anthrax vaccine (AV7909), lyophilized and liquid, both manufactured by Emergent BioSolutions, will be assessed and compared. AV7909 is an investigational vaccine that combines the currently licensed Anthrax Vaccine Adsorbed (AVA, BioThrax) with the adjuvant CPG 7909, an oligonucleotide.

Forty healthy young adults, 18 to 45 years old, inclusive, who meet all eligibility criteria, will be randomly allocated to one of two study groups in a 1:1 ratio: 20 will receive AV7909 as the thermostable lyophilized product and 20 will receive AV7909 as the liquid product. Stratification by age category and by sex will assure that near equal numbers of younger (18-30 years) and older (31-45 years) males and females will be assigned to each vaccine. The vaccines will be given intramuscularly in a 2-dose schedule, 2 weeks apart.

Safety will be assessed by evaluation of non-serious unsolicited Adverse Events, Serious Adverse Events (SAEs), Medically Attended Adverse Events (MAAEs), Adverse Events of Special Interest (AESIs) [the AESIs collected in this study are Potentially Immune-Mediated Medical Conditions (PIMMCs)], and by laboratory evaluations. SAEs, MAAEs, and AESIs will be collected from the time of study vaccination through approximately Day 380. Non-serious unsolicited AEs will be collected from Day 1 to Day 64, inclusive. Clinical laboratory evaluations for eligibility will be the following: specific hematology parameters, chemistry parameters, specific urine tests for drugs of abuse, and hemoglobin A1C. Also, an electrocardiogram will be performed at screening and reviewed by an investigator and cardiologist. The cardiologist will determine if any findings on the electrocardiogram are significant and thereby exclusionary. At approximately Day 29, laboratory tests for hematology and chemistries will be repeated.

Reactogenicity will be measured by the occurrence of solicited injection site and systemic reactions in the week after each study vaccination (Days 1 through 8 and target of Days 15 through 22, inclusive). The window for dose 2 includes Days 15 to 18. For participants who are vaccinated beyond Day 15, the study schedule will adjust so that a full week of reactogenicity data are collected, regardless. Any of these events that persist on Day 8 or Day 22 (or the final day of the second reactogenicity period) will be followed until resolution.

Immunogenicity testing will include performing serological assays to assess for toxin neutralizing antibodies (reported as ED50 and NF50), the gold standard assay for assessing response and protection following anthrax vaccines, prior to vaccination and on approximately Days 8, 15, 22, 29, 64, 195, and 380. Should the second dose of vaccine be given after Day 15 (the acceptable window is Days 15 to 18, inclusive) the remainder of the study schedule days shift accordingly, to maintain the intervals in the schedule. In addition, anti-PA IgG antibodies will be measured by ELISA from the serum of participants, on those same days.

# 4.2. Discussion of Study Design, Including the Choice of Control Groups

This study follows a randomized, parallel-group, double-blind control design. All subjects receive two doses of either liquid formulation of AV7909 or lyophilized formulation of AV7909, administered intramuscularly at Days 1 and 15.

# 4.3. Selection of Study Population

The study population for this clinical trial is 40 males and non-pregnant females, 18 to 45 years of age, inclusive, who are in good health and meet all eligibility criteria. The target population reflects the community at large at the participating VTEU site, the University of Maryland, Baltimore (UMB).

#### 4.4. Treatments

#### 4.4.1. Treatments Administered

Liquid and lyophilized formulations of AV7909, manufactured by Emergent BioSolutions, will be administered intramuscularly in a 2-dose schedule, 2 weeks apart. AV7909 is an investigational vaccine that combines the currently licensed Anthrax Vaccine Adsorbed (AVA, BioThrax) with the adjuvant CPG 7909, an oligonucleotide.

#### 4.4.2. Identity of Investigational Product(s)

See the study protocol for details of study product formulation.

#### 4.4.3. Method of Assigning Subjects to Study Arms (Randomization)

Enrollment and randomization will be performed through the enrollment module in the electronic data capture system, maintained by the SDCC.

Eligible subjects will be randomized and assigned in a 1:1 ratio to liquid AV7909 or lyophilized AV7909, with stratification by age category (18-30 years old and 31-45 years old) and by sex. The randomization is based on a variable blocked scheme to provide an approximately balanced allocation to the study arms within each age/sex stratum.

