## Test for difference in proportion responders:

 $H_0$ :  $p_c - p_e = 0$  – No difference in response probabilities

 $H_1$ :  $p_c - p_e \neq 0$  – difference in response probabilities

Table 13 illustrates the minimum detectable differences in the probability of responding (e.g., attaining seroconversion or  $NF_{50} \ge 0.56$  [seroprotection]) between participants who receive AV7909 as the lyophilized formulation or liquid formulation using a two-sided likelihood ratio test with 80% power and alpha = 0.05. It is assumed that up to 10% of subjects (N=2) will be excluded from the per-protocol analysis in each group. Seroconversion rates of 10% to 60% are considered.

Table 13: Minimum Detectable Difference in the Probability of Response with 80% Power

Re	Probability of Response in	80% Power					
	Comparator Group A	Minimal Detectable Difference	Probability of Response in Experimental Group B				
	0.10	0.39	0.49				
	0.20	0.43	0.63				
N = 18	0.30	0.43	0.73				
	0.40	0.42	0.82				
	0.50	0.39	0.89				
	0.60	0.35	0.95				

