#### 11.6.2 Safety Data

Summaries and analysis of safety data will be presented for the Safety Analysis Population. All summaries and analyses will be presented for all participants.

Solicited AEs will be summarized by severity after each study vaccination (through 7 days post study vaccination, Days 1 through 8 and Days 15 through 22) and as the maximum severity over all days. Additionally, solicited AEs will be analyzed by taking the most severe response over the follow-up period, dichotomizing into a binary variable (none versus mild, moderate, or severe) and using standard techniques, such as exact confidence intervals, to summarize the proportion of subjects reporting each symptom, any injection site symptom, and any systemic symptom. Summaries of solicited AEs will be presented for each study vaccination by treatment arm. The proportion of participants reporting symptoms may be compared between treatment arms using Chi-square or Fisher's exact test.

Unsolicited AEs will be coded by Medical Dictionary for Regulatory Activities (MedDRA®) for preferred term and system organ class (SOC). The numbers of SAEs, MAAEs, and AESIs

(PIMMCs) are likely to be small in this trial and will be reported by detailed listings showing the event description, MedDRA® preferred term and SOC, relevant dates (study vaccinations and AEs), severity, relatedness, and outcome for each event. Non-serious unsolicited AEs will be summarized as number and percentage of participants reporting at least one event in each MedDRA® preferred term and SOC, cross tabulated by severity and relationship to study product. Additionally, the proportion of participants and exact 95% confidence intervals of AEs in aggregate and by MedDRA® categories will be computed.

Clinical laboratory data will be summarized by severity for each visit and as the maximum over all post-study vaccination visits. Graphical presentations may include box plots.

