# 6.4. Covariates and Subgroups

TNA  $ED_{50}$  and  $NF_{50}$  and anti-PA IgG antibody responses will be summarized and stratified by sex and age category (18-30 years, 31-45 years). These analyses are considered exploratory as the study was not powered for subgroup analyses.

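### The SAP specifies no between-arm estimate of immunogenicity, and neither document names a between-arm method that uses the sex and age strata of the randomisation

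*SAP*

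**What the plan says.** **Design.** Under SAP 4.4.3, allocation between the two formulations is 1:1, "with stratification by age category (18-30 years old and 31-45 years old) and by sex". On how the blocks work, that section says: "The randomization is based on a variable blocked scheme to provide an approximately balanced allocation to the study arms within each age/sex stratum". Two binary factors give four strata. Block sizes are not stated. SAP 5 gives the size, "This study is planned to enroll a total of 40 subjects, with 20 subjects in each study arm", and the analysed number: "It is assumed that up to 10% of subjects (N=2) will be excluded from the per-protocol analysis in each group". That leaves 18 per arm.

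**Objective.** SAP 3.1.2 (and Protocol Table 1) sets an initial comparative estimate of immunogenicity as the secondary objective.

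**Planned immunogenicity output.** SAP 6.1 and 8 give each arm its own GMT or GMC and GMFR with a t-based interval, and its own proportions with a Clopper-Pearson interval. The shells for SAP Tables 21 to 32 have one column per arm and no column for a ratio or difference.

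**Between-arm methods named.** There are two. Protocol 11.4.3 and SAP 5 illustrate power "using a two-sided likelihood ratio test with 80% power and alpha = 0.05". Protocol 11.6.2 says that the proportions with solicited symptoms "may be compared between treatment arms using Chi-square" or Fisher's exact test. SAP 9.3.1 does not carry that test forward. Neither method is stratified.

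**Use of the strata.** SAP 6.4 and 8.2 summarise the antibody results by sex and, separately, by age category: "These analyses are considered exploratory as the study was not powered for subgroup analyses". SAP 9.3.1 does the same for solicited events (Tables 38 and 39).

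**The concern.** When allocation is blocked within strata, the design balances the stratification factors. A comparison that then ignores them leaves the between-stratum variance in the error term. If sex and age category predict titre, the interval is wider than the design requires. With 18 to 20 per arm, even a modest gain in precision is useful.

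The gap starts one step earlier. The objective is comparative, but the planned output is two columns of single-arm intervals that the reader must compare by eye. If someone later calculates a ratio of geometric means, the choice of model, with or without the randomisation factors, will be made after unblinding.

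**Working it through.** **1. The plan's own between-arm figure.** SAP Table 4 (Protocol Table 13) lists minimum detectable differences at n = 18 per arm. I enumerated both binomials exactly and rejected when the unstratified likelihood-ratio statistic exceeded 3.841.

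| Comparator rate | Stated difference | Experimental rate | Exact power |
|---|---|---|---|
| 0.10 | 0.39 | 0.49 | 0.803 |
| 0.20 | 0.43 | 0.63 | 0.807 |
| 0.30 | 0.43 | 0.73 | 0.799 |
| 0.40 | 0.42 | 0.82 | 0.795 |
| 0.50 | 0.39 | 0.89 | 0.792 |
| 0.60 | 0.35 | 0.95 | 0.811 |

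The table reproduces to within about one percentage point of 80%. It is therefore an unstratified calculation, as its wording implies.

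**2. What adjustment would do to an interval for a difference in mean log titre.** Inputs from the documents: 18 per arm, so N = 36, and two binary factors. Assumed: R², the share of log-titre variance explained by sex and age category. The unadjusted model has 36 − 2 = 34 degrees of freedom. The model with formulation, sex and age category has 36 − 4 = 32.

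Width ratio, adjusted to unadjusted = [t(0.975, 32) / t(0.975, 34)] × √(1 − R²) = (2.0369 / 2.0322) × √(1 − R²) = 1.0023 × √(1 − R²).

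| R² (assumed) | Adjusted / unadjusted | Unadjusted wider by |
|---|---|---|
| 0 | 1.002 | −0.2% |
| 0.05 | 0.977 | 2.4% |
| 0.10 | 0.951 | 5.2% |
| 0.20 | 0.896 | 11.5% |

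The ratio does not depend on the titre SD. Break-even is R² = 1 − (2.0322 / 2.0369)² ≈ 0.5%. Fitting all four strata as separate cells moves it to about 0.7%.

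**3. Simulation check.** 6,000 trials per setting, 36 participants, four equally likely strata, blocks of 2 and 4 (strata proportions and block sizes assumed).

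| R² | Adjusted / unadjusted | Unadjusted coverage | Adjusted coverage |
|---|---|---|---|
| 0 | 1.004 | 94.9% | 95.0% |
| 0.05 | 0.978 | 95.3% | 95.0% |
| 0.10 | 0.951 | 95.4% | 94.6% |
| 0.20 | 0.895 | 96.8% | 95.1% |

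The simulation agrees with the formula and gives 1 / 0.895 = 1.117, so the R² = 0.20 row is about 12%. Unadjusted coverage is at or above nominal within simulation error, so the unadjusted interval is valid to conservative. The cost of adjusting when R² = 0 is 0.2% by formula and 0.4% to 0.5% in simulation, which also reflects small leftover imbalance.

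**4. How much imbalance the blocking leaves.** 40 participants, four equally likely strata (assumed), absolute difference between arms in the proportion of one sex.

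| Scheme | Mean | 95th percentile |
|---|---|---|
| Stratified, blocks 2/4 | 3.2 points | 9.8 points |
| Stratified, blocks 4/6 | 3.9 points | 10.0 points |
| Unstratified 20:20 | 12.6 points | 30.0 points |

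Removing two participants per arm at random, as a stand-in for the per-protocol exclusions, raises the first row to about 5 and 12 points.

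**The case against.** The strongest reply is that nothing planned is harmed. The trial is stated to be estimation only, with no formal hypothesis (Protocol 11.2, SAP 5 and 6.8). Every planned interval is for one arm or for all participants pooled, so there is no comparative interval to widen. The likelihood ratio test is a planning illustration. The Chi-square or Fisher test is optional and would give a p-value, not an interval. The widths above concern a difference in mean log titre, whereas both named methods concern proportions. The R² values, block sizes and stratum sizes are assumed, and 20% is a lot to expect from sex and a two-level age split in healthy adults aged 18 to 45. The strata are also used, in the subgroup summaries.

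All of that stands, and it limits the point. A reader might infer two stronger claims that the documents do not support:

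- **That the planned intervals are too wide.** They are within-arm or pooled, and omitting the strata from a between-arm analysis does not affect them.
- **That chance imbalance in sex and age goes uncorrected.** Blocking within strata is itself the control and keeps the imbalance to a few percentage points under the assumed block sizes. Adjusting for these factors would not touch imbalance in others.

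The objection does not remove the mismatch between a comparative objective and a plan with no comparative estimate. The absence of a hypothesis is no reason to omit an estimate. The subgroup tables give per-arm results within one factor at a time, which is not a stratum-adjusted comparison.

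**Conclusion.** The point holds in a limited form. The SAP leaves its comparative secondary objective without a between-arm estimate, and the randomisation factors enter no between-arm method in either document. This is an omission and a possible gain in precision, not an error in a planned analysis. An unadjusted comparison would not be biased.

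The size is conditional. At 18 per arm, ignoring the strata would widen an interval for mean log titre by about 2%, 5% or 12% at R² of 5%, 10% or 20%. The documents give no R², so any value in or below that range is possible. Adjusting when the factors are not prognostic costs about 0.2% to 0.5%, and it pays once R² passes roughly 0.5%. That asymmetry makes adjustment the sensible default. No gain has been calculated for seroconversion, seroprotection or solicited events, and none is claimed.

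**What to change.** In SAP 6.4 and 8, add for log10 ED50, log10 NF50 and log10 anti-PA IgG at each post-vaccination visit a linear model with formulation, sex and age category. Report the back-transformed formulation effect as a lyophilized/liquid geometric mean ratio with 95% CI. Label it descriptive, with no hypothesis test. Present it for the mITT and PP populations that SAP 8.2 already reports, and keep the per-arm and subgroup summaries unchanged.

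A stratified difference in proportions is optional. If equal strata are assumed, each arm has only about 18 / 4 = 4.5 participants per stratum, so empty cells are likely. It should be added only with a rule, fixed before unblinding, that says which strata are merged and when.

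The cost is SAP wording, one added table shell per assay and a few lines of code. The factors are already recorded for randomisation, and trial conduct does not change. The statistical cost is two degrees of freedom.
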